9.2.2 Rationale for Study Population

This study will enroll subjects with EAD including MCI due to AD and the early stages of mild AD. It is considered that this population is the most likely to benefit from the administration of a BACE1 inhibitor such as elenbecestat (E2609). This is because as AD progresses to the clinical diagnosis of dementia and more severe stages of the disease with the loss of functional capabilities, the amyloid load in the brain has already reached a plateau and significant neurodegeneration has occurred ([Jack et al., 2011](#)). There is a growing consensus within the AD field that it may be necessary to initiate disease-modifying treatments earlier, before the onset of clinical dementia ([Aisen et al., 2010](#)). As a consequence, attempts to slow disease progression with elenbecestat (E2609) are most likely to succeed at an earlier stage at which there is limited neurodegeneration; therefore, the

selected population for this study is subjects with EAD including MCI due to AD and the early stages of mild AD.

Subjects who do not meet all of the inclusion criteria or who meet any of the exclusion criteria will not be eligible to receive study drug.

9.2.3 Rationale for Clinical Endpoints

The CDR is a clinical global rating scale requiring the interviewing of both the subject and a study partner who knows and has contact with the subject. The CDR is a clinician directed assessment of both cognition and function, and is intended to capture the state and therefore the disease stage of the individual. The CDR has been proposed as an acceptable approach for following disease progression and confirming treatment effects in AD. The cumulative score or CDR-SB is a well-described, validated, and reliable measure of change through the course of AD and has been proposed as a suitable single outcome measure for AD trials in dementia and pre-dementia populations (FDA 2013 AD Guidelines, EMA 2016 AD Guidelines).

The ADAS-Cog is the most widely used cognitive scale in AD clinical studies (Rosen, et al., 1984). The 14-item version will be used in the present study since it is considered more sensitive for less impaired populations such as MCI/Prodromal and mild AD subjects (Fleisher, et al., 2007). Furthermore, a separate endpoint for the ADAS-cog₁₄ immediate recall and delayed recall subtests is included.

The MMSE is a cognitive instrument commonly used for screening purposes, for staging of disease severity and is often measured longitudinally in AD clinical studies to follow disease progression and treatment effects (Folstein, et al., 1975).

The FAQ collects information on 10 items concerned with performing daily tasks necessary for independent living. The FAQ is considered as a better indicator of clinical meaningfulness than cognitive change as it reflects the subject's functional state and should correlate well with AD progression.

The ISLT is sensitive to memory impairment that characterizes both AD and MCI (Lim, et al., 2012a). In MCI subjects, the magnitude of the impairment observed on the total recall and delayed recall trials of the ISLT was consistent with the magnitude of impairment expected to occur. It is sensitive to the episodic memory impairment that characterizes MCI with high amyloid (unpublished data from the Australian Imaging, Biomarker & Lifestyle Flagship Study of Ageing study). Data are robust across different groups of healthy older individuals, and accordingly criteria used for defining abnormal performance are reliable (Thompson, et al., 2011; Lim, et al., 2012a; Lim, et al., 2012b). Data computations indicate that the ISLT will be sensitive to the expected changes in amyloid-related memory dysfunction with elenbecestat (E2609) treatment.

9.2.4 Rationale for Biomarkers

The biomarker strategy for this study includes the following aims:

- To determine whether elenbecestat (E2609) is superior to placebo on brain amyloid levels at 24 months as measured by amyloid PET in subjects with EAD
- To determine whether elenbecestat (E2609) is superior to placebo on CSF t-tau and p-tau levels at 24 months in subjects with EAD
- To determine whether elenbecestat (E2609) is superior to placebo on CSF amyloid beta (A β) levels at 24 months in subjects with EAD
- To determine whether elenbecestat (E2609) is superior to placebo on hippocampal atrophy at 24 months in subjects with EAD as measured by changes in hippocampal volume using vMRI
- To evaluate whether elenbecestat (E2609) is superior to placebo in preserving connectivity as measured by fMRI
- To explore the relationship between exposure (in CSF, plasma) of elenbecestat (E2609) with potential biomarkers of AD as deemed appropriate

CSF biomarkers and amyloid PET assessments on disease progression at 24 months (and at 12 months for amyloid PET) will be evaluated in a substudy of subjects. The CSF substudy is limited to a single timepoint at 24 months to acknowledge the additional burden to the subject that a lumbar puncture procedure entails. Participation in the substudies is optional and will require specific consent.

These aims are discussed below in the context of the individual biomarker assessments to be used in this study.

Briefly, the biomarkers that will be utilized and assessed during this study are:

Soluble Biomarkers in CSF

A β (1-x) captures the effect on the total A β component; therefore, the measurement of this A β isoform most appropriately represents the total pharmacologic effect (A β [1-40] + A β [1-42] and other C-terminally truncated A β peptides such as A β [1-38]) on inhibition of BACE enzyme cleavage.

A β (1-42) measurements in CSF have shown high correlation with results using 11C-Pittsburgh Compound B (PiB), suggesting that CSF A β (1-42) reflects fibrillar A β content ([Grimmer, et al., 2009](#)). The aggregation of A β peptides into plaques, and subsequent retention of peptides in the brain parenchyma, accounts for reduced availability of A β to diffuse into the CSF. The decreases seen in AD due to amyloid plaque deposits are related to this decrease.

T-tau and p-tau are sensitive markers of axonal and neuronal degeneration (t-tau) and NFTs (p-tau), and have been demonstrated to increase in parallel with disease progression (Chintamaneni, et al., 2012).

Baseline levels of A β (1-42), t-tau, and p-tau will also help elucidate the extent of AD pathology at study entry, and can be combined with *ApoE4* genotype in addition to the baseline imaging variables to help explain differences in treatment response between subjects.

Amyloid PET

Amyloid PET imaging will be performed in this study for 2 primary reasons: 1) as one of the methods of confirming the presence of amyloid pathology in the brain of subjects with EAD including MCI due to AD and the early stages of mild AD at study entry (the other method being measurement of A β (1-42) in the CSF); and 2) to evaluate the effects of elenbecestat (E2609) on amyloid levels in the brain at 12 and 24 months, both by whole brain analysis (the average of 5-6 cortical regions) and brain region analysis. This second part is an optional longitudinal substudy.

vMRI and fMRI

vMRI performed at 12 and 24 months will be used to evaluate the effects of elenbecestat (E2609) on rates of atrophy across the treatment groups and to provide support that effective treatment is associated with modification of disease progression. A large body of data has shown that structural MRI reliably tracks disease progression in AD. Atrophy tends to occur preferentially in the lateral temporal and posterior parietal regions during the early stages of disease and progresses towards the anterior regions of the brain (frontal cortex) in its later stages. For this reason hippocampal volume has been selected as a secondary endpoint, and it is predicted that clinically efficacious doses will be associated with a slowing in the rate of hippocampal atrophy compared to rates observed in the placebo. Whole brain, ventricular volumes, and possibly other regions deemed to be of scientific value will also be measured.

Task free fMRI can be used to assess the integrity of functional networks within the brain to help determine effects of disease on brain function. fMRI eliminates performance confounds that are seen with task based functional neuroimaging. fMRI requires an additional 7 to 10 minutes of scan time for acquisition of the data. fMRI data will be used to generate connectivity maps based on critical anatomical regions (eg, precuneus, inferior frontal sulcus) which can then be used within subject to determine the effect of elenbecestat (E2609) on preserving connectivity known to degrade with progression of AD.

Exploratory Biomarkers

Exploratory biomarkers in plasma may be measured as validated assays (such as neurofilament light [NFL], neurogranin [Ng], or visinin like protein 1 [VILIP1]) become available. (revised per Amendment 01)

9.3 Selection of Study Population

Approximately 1330 subjects with EAD including MCI due to AD and the early stages of mild AD will be enrolled across up to approximately 350 centers worldwide. Randomization will be stratified according to region (7 levels), clinical dementia staging, with no more than approximately 25% of the randomized subjects diagnosed with the early stages of mild dementia due to AD, and concurrent AD medication use.

Subjects who do not meet all of the inclusion criteria or who meet any of the exclusion criteria will not be eligible to receive study drug.

9.3.1 Inclusion Criteria

Subjects must meet all of the following criteria to be included in this study:

1. MCI due to AD or Mild AD according to the National Institute of Aging – Alzheimer’s Association (NIA-AA) core clinical criteria and must have all of the following:
 - a. MMSE score equal to or greater than 24
 - b. CDR global score of 0.5
 - c. CDR Memory Box score of 0.5 or greater
2. A history of subjective memory decline with gradual onset and slow progression over the last 1 year before Screening; this MUST be corroborated by a study partner
3. Cognitive impairment of at least 1 SD from age-adjusted norms in total recall or delayed recall on the ISLT.
4. Positive biomarker for brain amyloid pathology as indicated by at least 1 of the following:
 - a. PET assessment of amyloid imaging agent uptake into brain. Note: amyloid PET screens will be performed according to local regulatory guidelines and thus may be restricted for those subjects who are not suitable for LP to obtain CSF for testing of eligibility.
 - b. CSF assessment of A β (1-42)

NOTE: Subjects may undergo both the amyloid PET and CSF assessments, but need a positive amyloid result in only 1 of the 2 procedures to confirm eligibility. Subjects who consent to amyloid PET or CSF for eligibility purposes are not required to participate in the amyloid PET or CSF longitudinal substudies. Use of a historical amyloid PET (conducted within 12 months before the planned date of randomization) is acceptable for determination of eligibility but will not suffice for the baseline assessment if the subject wishes to consent to the amyloid PET longitudinal substudy. The historical imaging data must be made available to the sponsor.
5. Male or female subjects between 50 and 85 years of age, inclusive at the time of consent
6. If receiving an AChEI or memantine or both for AD, must be on a stable dose for at least 12 weeks prior to Randomization. Treatment-naïve subjects with AD can be entered into the study.

7. Subjects must have been on stable doses of all other (ie, non-AD related) permitted concomitant medications for at least 4 weeks prior to Randomization, except for medications which are administered as short courses (eg, up to 3 weeks unless discussed and agreed with Medical Monitor) of treatment (eg, anti-infectives, oral steroids) or which are to be used on a Pro re nata (PRN) basis. Subjects who require a short course of treatment, such as anti-infectives or oral steroids, may be randomized once the acute illness has completely resolved, even if the concomitant medication continues.
8. Must have an identified study partner (defined as a person able to support the subject for the duration of the study and who spends at least 8 hours per week with the subject). The study partner must provide written informed consent. In addition, this person must be willing and able to provide follow-up information on the subject throughout the course of the study. This person must, in the opinion of the investigator, spend sufficient time with the subject on a regular basis such that they can reliably fulfill the requirements of being a study partner. A study partner need not be living in the same residence with the subject. For such a study partner not residing with the subject, the investigator has to be satisfied that the subject can contact the study partner readily during the times when the study partner is not with the subject. Study partners need to provide input to the following assessments: CDR, FAQ, EQ-5D, QOL-AD, Zarit's Burden Interview, NPI-10, and the clinical assessment of suicidality. Consideration can occur for the investigator to decide whether the study partner can provide information over the telephone or whether the study partner must attend the study visits in person with the subject.

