- Thyroid stimulating hormone (TSH) above normal range. Other tests of thyroid function with results outside the normal range should only be exclusionary if they are considered clinically significant by the investigator (this applies to all subjects whether or not they are taking thyroid supplements)
- Abnormally low (below LLN) serum Vitamin B12 levels (if subject is taking Vitamin B12 injections, level should be at or above the LLN)

10. Subjects at risk of increased risk of infection, specifically:

- Subjects with chronic viral hepatitis, a history of active tuberculosis disease (TB), ophthalmic shingles or ocular herpes simplex virus (HSV) infection
- Any active infection within the last 4 weeks before randomization. For such cases, the timing of randomization can be extended (up to 4 weeks) to allow the infection to resolve
- Any immunological disease which is not adequately controlled, or which requires treatment with biologic drugs during the study. History of immunoglobulin deficiency or other immunodeficiency disorders (including subjects known to be HIV positive)

11. Have received any live/live attenuated vaccine in the 3 months before randomization

12. Any chronic inflammatory disease that is not adequately controlled or that requires systemic or ocular immunosuppressive or immunomodulatory therapy.

NOTE: The following subjects do not need to be excluded:

- Subjects with seasonal or perennial allergic rhinitis, asthma, or chronic obstructive pulmonary disease where the condition is considered to be stable and adequately controlled by inhaled steroids.

- Hashimoto's thyroiditis but who are stable on thyroid replacement therapy and not on systemic immunosuppressive therapy.
- Cutaneous manifestations of immunological disease that do not require systemic immunosuppressive therapy or systemic immunomodulatory therapy (ie, topical steroid treatment is permitted)

13. Any other clinically significant abnormalities, such as:

- Physical examination, vital signs, laboratory tests or ECG at Screening or Baseline which in the opinion of the investigator require further investigation or treatment or which may interfere with study procedures or safety.
- Other medical conditions (eg, cardiac, respiratory, gastrointestinal, psychiatric, renal disease) which are not adequately and stably controlled, or which in the opinion of the investigator(s) could affect the subject's safety or interfere with the study assessments (revised per Amendment 01)

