9.4.7 Prior and Concomitant Therapy

Any medication (including over-the-counter medications) or therapy administered to the subject prior to the study (within 6 months of randomization) and during the study (starting at the date of informed consent) will be recorded on the Prior & Concomitant Medication eCRF or Non-Pharmacological Procedures eCRF. The investigator will record on the Adverse Event eCRF any AE for which the concomitant medication/therapy was administered. If the concomitant medication/therapy is being administered for a medical condition present at the time of entry into the study, the investigator will record the medical condition on the Medical History and Current Medical Condition eCRF.

Listings of prohibited and permitted drugs are provided in [Appendix 2](#) (Prohibited medications are presented in [Listing 1](#), [Listing 2](#), and [Listing 3](#). Medications that are permitted with restrictions are listed in [Listing 4](#), [Listing 5](#), and [Listing 6](#)).

The following agents are not permitted before randomization (specific time frames are shown below) and until the last visit during the treatment period: (revised per Amendment 01)

- a) Immunoglobulin therapy and biologic drugs are not permitted within 6 months before Screening and until the last visit during the treatment period (revised per Amendment 01)
- b) Systemic or ocular immunosuppressive or immunomodulatory drugs are not permitted for a period of 5 half-lives or 60 days (whichever is longer) before randomization and until the last visit during the treatment period (revised per Amendment 01)
- c) Moderate to strong inhibitors of carboxylesterase 2 (CES2) enzyme activity are not permitted for a period of 5 half-lives or 7 days (whichever is longer) before

randomization and until the last treatment visit. Simvastatin use is permitted only with QD evening administration.

- d) Live/live attenuated vaccines are not permitted within 3 months before randomization and until the last treatment visit (this does not apply to non-live/inactivated vaccines) (revised per Amendment 01)

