Appendix 2 List of Permitted and Prohibited Prior/Concomitant Medications

Prohibited medications are shown in [Listing 1](#), [Listing 2](#), and . Medications permitted with restrictions are listed in [Listing 4](#), [Listing 5](#), and [Listing 6](#). These may not be all-inclusive listings. Please contact the medical monitor(s) if the investigators have any questions or concerns regarding any medication not listed that your subjects may be taking before enrollment or start during the course of the E2609-G000-302 study.

Antibiotics, analgesics, and anti-inflammatory drugs intended for short courses of treatment are permitted and do not need to follow the restrictions of [Listing 6](#) for a stable dose of 4 weeks before Baseline. If these medications may affect cognitive function but the medications are clinically indicated, then cognitive testing should not take place until at least 72 hours after the last dose of the course of treatment.

Prohibited Prior/Concomitant Medications

Listing 1 Prohibited Medications Within 5 Half Lives or 7 Days, Whichever is Longer, Before Randomization and Until the Last Visit During the Treatment Period

Moderate to Strong Inhibitors of Carboxylesterase 2 (CES2) Enzyme Activity
Generic name
Loperamide
Orlistat
Telmisartan
Fenofibrate
Carvedilol
Manidipine
Diltiazem
Verapamil

NOTE: Simvastatin use is permitted only with once daily evening administration.

Listing 2 Prohibited Medications Within 5 Half Lives or 60 Days, Whichever is Longer, Before Baseline and Until the Last Visit During the Treatment Period

Systemic or Ocular Immunosuppressants^a and Immunomodulatory Drugs (revised per Amendment 01)	
Prednisolone	Deltasone, Prednicot, Prednisone Intensol, Rayos, Sterapred, Sterapred DS
Methylprednisolone	Medrol, Meprolone
Dexamethasone	Decadron, Dexasone, Diodex, Hexadrol, Maxidex
Azathioprine	Azasan, Imur
Mycophenolate	CellCept, Myfortic
Fingolimod	Gilenya
Methotrexate	Trexall
Ciclosporine	Gengraf, Neoral

Prohibited Medications Within 6 Months Before Screening and Until the Last Visit During the Treatment Period (revised per Amendment 01)

Immunoglobulin Therapy and Biologic Drugs (revised per Amendment 01)	
Ranibizumab	Lucentis
Bevacizumab	Avastin
Infliximab	Remicade
Etanercept	Enbrel
Adalimumab	Humira
Omalizumab	Xolair
Efalizumab	Raptiva

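### Inclusion criterion 7 allows randomisation during a short course of oral steroids, which section 9.4.7(b), Listing 2 and exclusion criterion 18 together prohibit

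*Protocol*

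**What the plan says.** Two sets of passages in the current protocol text (as revised per Amendment 01) bear on oral steroids.

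**Passages that allow them as a short course**
- Section 9.3.1, criterion 7, exempts from the 4-week stable-dose requirement medicines given as "short courses (eg, up to 3 weeks unless discussed and agreed with Medical Monitor) of treatment (eg, anti-infectives, oral steroids". It adds: "Subjects who require a short course of treatment, such as anti-infectives or oral steroids, may be randomized once the acute illness has completely resolved". Read to its end, the sentence says that they "may be randomized once the acute illness has completely resolved, even if the concomitant medication continues". The synopsis repeats both statements.
- Section 9.4.7, in its paragraph on other medicines, again gives oral steroids as an example of a short course exempt from the 4-week stable-dose requirement.
- The opening text of Appendix 2 says: "Antibiotics, analgesics, and anti-inflammatory drugs intended for short courses of treatment are permitted". It then releases these from the stable-dose rule of Listing 6.

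**Passages that bar them**
- Section 9.4.7(b) says: "Systemic or ocular immunosuppressive or immunomodulatory drugs are not permitted for a period of 5 half-lives or 60 days", whichever is longer, before randomisation. The bar continues to the final visit of the treatment period.
- Listing 2 of Appendix 2, headed "Systemic or Ocular Immunosuppressants" and immunomodulatory drugs, names prednisolone, methylprednisolone and dexamethasone. It sets the same window, counted from Baseline. Its footnote spares only topical and inhaled products with little systemic exposure.
- Section 9.3.2, criterion 18, excludes anyone taking a prohibited medicine. Section 9.3 states that meeting any exclusion criterion makes a subject ineligible for study drug.

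**The concern.** One set of passages tells a site that it may randomise a subject who is still taking oral steroids. The other tells it that the same subject must have been free of them for at least 60 days and must stay free of them on treatment. Both are current instructions, and neither refers to the other.

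The drug class makes this more than an editorial matter. Section 7.1 reports immunologic findings in monkeys and some evidence of CD4 reduction at 50 to 100 mg in the multiple-dose study; the trial dose is 50 mg. Under section 9.3.3, a confirmed lymphocyte count below 800/mm³ leads to interruption of study drug, and a second confirmed occurrence within 6 months leads to permanent discontinuation. The protocol itself treats systemic immunosuppressants as something to keep out of the trial. With up to approximately 350 sites, whether a subject enters while taking one should not depend on which page the site reads.

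**Working it through.** There is no sample size, power or error rate to recompute. The check takes one subject through both sets of rules.

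**Test case.** A subject develops an acute illness during screening, is given a short course of oral prednisolone, recovers fully, and is still taking the tablets at Visit 2 (Day 1, randomisation).

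| Step | Source | Result for this subject |
|---|---|---|
| 1 | Section 9.3.1, criterion 7 | Oral steroids are a named example and the illness has resolved, so randomisation may proceed on treatment |
| 2 | Section 9.4.7(b) | The class is barred for max(5 half-lives, 60 days), so for at least 60 days, before randomisation |
| 3 | Appendix 2, Listing 2 | Prednisolone is named; an oral tablet is neither topical nor inhaled, so the footnote does not apply |
| 4 | Section 9.3.2, criterion 18 | The subject is taking a prohibited medicine and is excluded |
| 5 | Section 9.3 | Any exclusion criterion is decisive, so the subject is not eligible for study drug |

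**Size of the conflict.** The minimum steroid-free interval before randomisation is 0 days under criterion 7. Under section 9.4.7(b) and Listing 2 it is at least 60 days. The gap is at least 60 − 0 = 60 days.

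**During treatment.** The prohibition runs on to the final treatment-period visit. A course that continues past Visit 2, as criterion 7 allows, therefore breaches the on-treatment bar from the first day as well as the pre-randomisation window.

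**Three details**
- Section 9.4.7(b) names only the class; Listing 2 is what places oral corticosteroids in it.
- Criterion 18 states no window of its own; the 60 days come from section 9.4.7(b) and Listing 2.
- Section 9.4.7(b) counts from randomisation and Listing 2 from Baseline; for this purpose both are Visit 2.

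**Not an artefact of the amendment.** Version 1.0 of the protocol already names oral steroids in criterion 7 and lists the same three steroids as prohibited. Amendment 01 left the conflict in place.

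**The case against.** Several readings might remove the conflict.

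1. *Criterion 7 covers only permitted medicines.* Its first sentence does say so. But it then gives oral steroids as an example and expressly allows randomisation while they continue. If they were never permitted, both statements would have no content.
2. *Appendix 2 already allows short courses of anti-inflammatory drugs.* This is the best counter-argument, and it suggests that a short-course allowance may have been intended and a cross-reference or footnote left out. But the sentence does not name steroids, the restriction it goes on to waive is that of Listing 6, and Listing 2 has no short-course exception.
3. *The medical monitor can resolve it.* Appendix 2 sends sites to the monitor about medicines that are not listed. These steroids are listed. The monitor clause in criterion 7 concerns courses longer than about 3 weeks.
4. *The exclusions simply prevail.* That gives a workable answer under section 9.3, but it leaves criterion 7 and part of section 9.4.7 giving sites a wrong instruction.

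The objection to the size of the harm largely stands. A screening lymphocyte count below the lower limit of normal or 800/mm³, whichever is higher, is already exclusionary. Hematology is drawn at every scheduled visit from Visit 2. A low count must be confirmed on repeat testing before study drug is interrupted. The trial is double-blind, and the primary analysis uses the full analysis set without regard to adherence, so differing site practice before randomisation would apply to both arms alike.

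**Conclusion.** The contradiction is real and sits within one version of the protocol. For short-course oral steroids the required steroid-free interval is either 0 days or at least 60 days, and the same subject can satisfy criterion 7 and be excluded under criterion 18. The conclusion rests on the text alone. The number of subjects affected is not given and cannot be derived.

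A reader might infer more than the documents support:

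- **Infection.** Exclusion criterion 10 bars "Any active infection within the last 4 weeks before randomization", which could be set against criterion 7 as 28 days versus 0. But criterion 10 goes on to allow randomisation to be put back so that the infection can resolve, and resolution is also the condition in criterion 7. The criteria apply together, so a site can satisfy both by waiting. This is not a firm contradiction.
- **Section 9.4.7 permitting randomisation on continuing medication.** Only criterion 7 and its synopsis copy say that. Section 9.4.7 merely exempts short courses from the stable-dose requirement.
- **Exclusion criterion 12.** It concerns chronic inflammatory disease, and no conflict with it is shown.
- **The per-protocol set.** Section 9.7.1.2 leaves its criteria to the statistical analysis plan, so no fault can be found on that score here.
- **The primary comparison.** No bias, loss of power or inflation of type I error is shown.

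This is therefore an eligibility and safety inconsistency that should be corrected, not a defect in the analysis.

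**What to change.** The sponsor should reconcile five places so that one rule governs short-course systemic steroids, both before randomisation and during treatment:

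- inclusion criterion 7 (section 9.3.1 and the synopsis);
- section 9.4.7, both item (b) and the paragraph on short courses, with the matching synopsis text;
- the short-course sentence at the start of Appendix 2;
- Listing 2 and its footnote;
- exclusion criterion 18, which takes its meaning from the others.

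Whether the single rule allows such courses, and on what terms, is a clinical decision for the sponsor. This review does not propose one. The cost is protocol amendment wording and a letter to sites. No change to the sample size or the primary analysis follows.
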